4.4 Trial Design

This will be an investigator-initiated, prospective, open label, parallel group, multi-center, randomized controlled trial (RCT). Participants will be randomized in a 1:1-ratio, using stratified (local) randomization by study center (UZ Leuven or AZ Sint-Lucas Brugge), to either a control group or an intervention group (n = 120 participants in total, 60 in each group). The randomization schedule will be based on center-specific, computer-generated sequences programmed in Research Electronic Data Capture (REDCap), ensuring allocation concealment.

Following randomization, the intervention group will be re-randomized (via computer-generated simple randomization in REDCap) into two arms in a 1:1 ratio (n = 30 participants in each arm).

Participants in intervention arm A will be asked to complete the RAID questionnaire once a week via the Sidekick app, compared to once a month in intervention arm B.

The control group will be followed according to usual care standards. This includes informal screening for psychosocial wellbeing and illness perceptions during outpatient clinic visits, with referral to specific allied health professionals for additional education or non-pharmacological support if needed. The scores derived from questionnaires that form part of the study design can be

[figure not shown]
used as a guide for these discussions. As part of standard care, participants in both the control group and the intervention group will also receive a standardized educational leaflet about RA (attached as additional file), as is already available in the clinic and via the website of patient organization **ReumaNet**.

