5.2 Exclusion criteria

Since the study intervention does not include an IMP, no strict exclusion criteria are defined other than the abovementioned inclusion criteria. However, participants will be excluded from analyses if they do not provide any questionnaire data at either of the two study visits, or, for the intervention group, if they fail to use the Sidekick Health application at least once (= dropouts).

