6.1 By visit

Visit 1 (screening and baseline):

- Recruitment of eligible participants after informed consent at the Rheumatology outpatient clinic of the participating centers.
- Two-step randomization, as described above, into a control group and an intervention group (1:1), which will in turn be re-randomized in a 1:1 ratio into a weekly RAID arm and a monthly RAID arm.
- Downloading Sidekick Health app (intervention group only).
- Collection of demographic and disease-related characteristics for included patients: age, sex, RF and ACPA status, radiographic erosions, disease duration, current DMARD-therapy, prior DMARD-therapy, BMI, smoking status, education level.
- Collection of relevant medical and surgical history and comorbidities.
- Physical examination, including TJC28 and SJC28, measurement of weight and height.
- Patient's and Physician's global assessment (VAS).

- Participants in both the control and intervention groups will be asked to complete the following questionnaires considering self-efficacy (ASES), patient-reported outcomes (RAID), daily functioning (HAQ), pain catastrophizing (PCS), physical activity (IPAQ-S) and sleep quality (PSQI). Questionnaires will be completed in MyNexuzHealth (an online patient communication platform used by the University Hospitals Leuven Belgium) or, if not possible, in a pen-and-paper form at the outpatient clinic.

- Self-efficacy: The ASES is a patient-reported questionnaire (25) consisting of 20 items to measure one's arthritis-specific self-efficacy across 2 subscales: self-efficacy for managing pain (PSE, range 5-50), and self-efficacy for controlling other symptoms (OSE, range 6-60). Both scores can be summed to derive a total ASES-score (range 11-110).
- Patient-reported outcomes: The RAID questionnaire is a patient-derived differentially weighted 7-item tool assessing pain, functional disability, fatigue, sleep, coping, physical and emotional well-being.
- Daily functioning: The HAQ is a self-administered questionnaire, that assesses the ability in performing daily life activities and measures the functional impact of rheumatoid arthritis (26). The HAQ is routinely collected at the rheumatology outpatient clinic at University Hospitals Leuven.

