9.2 Analysis

Analyses will be carried out according to the intention-to-treat (ITT) principle, implying that participants will be analyzed based on the group they were originally assigned to.

In this study, the ITT population will consist specifically of all patients in the intervention group who effectively downloaded and installed the Sidekick application at the baseline visit, and all patients assigned to the control group. As stated above, participants in the intervention group will be re-randomized to intervention arm A or B, constituting two additional ITT populations that will only be analyzed exploratorily.

Per protocol (PP) analyses will be carried out as sensitivity analyses, including only those patients who completed the follow-up visit.

The variables described above in sections 4-6 will be extracted from the electronic medical patient file that is employed in all participating centers (KWS). Additionally, user behavior statistics and data actively logged by the patients in the app will be collected and provided for analysis in pseudonymized form by Sidekick Health. The primary and secondary outcome data of this study will be collected via questionnaires on the MyNexuzHealth app, or if not possible in pen-and-paper format at the outpatient clinic. All study-related information will be assembled and prepared for further analysis in an electronic CRF developed in REDCap. P-values <0.05 will be considered as statistically significant for all analyses. Missing data will be handled with multiple imputation by chained equations when data can be assumed to be missing at random. Descriptive statistics for baseline participant characteristics will be provided as means (\pm SD), medians (IQR) or proportions depending on data distribution.

Primary endpoint

The difference in mean change of total ASES (Arthritis Self-Efficacy Scale) score from baseline to week 16 \pm 2w in the intervention group when compared to the control group will be evaluated with an unpaired t-test or Wilcoxon rank sum test depending on distribution of the ASES-score. As a sensitivity analysis, we will additionally assess the difference between groups in week 16 scores using ANOVA adjusted for the baseline score. Furthermore, differences in the pain and other symptoms subscales of the ASES will be presented separately.

Secondary endpoints

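### The population labelled ITT leaves out intervention participants who did not install (9.2) or never used (5.2) the app; the two rules conflict, only one arm can fail them, and no all-randomised analysis is planned

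*Combined protocol and SAP*

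**What the plan says.** Section 9.2 (Analysis) opens with the ITT principle: "participants will be analyzed based on the group they were originally assigned to". The next paragraph then gives the ITT population as "all patients in the intervention group who effectively downloaded and installed the Sidekick application at the baseline visit, and all patients assigned"; the closing words refer to controls, who are all kept.

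Section 5.2 (Exclusion criteria) adds two rules for removal from analyses. One applies to both arms: "participants will be excluded from analyses if they do not provide any questionnaire data at either of the two study visits". The other applies to one arm: "for the intervention group, if they fail to use the Sidekick Health application at least once (= dropouts").

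The only other population in 9.2 is per protocol, used for sensitivity analyses, "including only those patients who completed the follow-up visit". The further sensitivity analysis, week-16 scores adjusted for baseline, names no population of its own.

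The trial is open label (4.4). The flowchart (4.6) and the visit 1 list (6.1) place randomisation before the app step, which 6.1 gives as "Downloading Sidekick Health app (intervention group only"). On outcome data, 9.2 says: "The primary and secondary outcome data of this study will be collected via questionnaires on the MyNexuzHealth app", with paper forms as the fallback.

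**The concern.** An ITT comparison is protected because group membership is fixed at randomisation. Here, intervention participants also have to do something after they know their allocation, and controls do not. Controls who would not have installed or opened the app cannot be identified, so they stay in. If people who do not take up the app differ in prognosis, the two analysed groups differ for a reason other than the app.

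The two rules also disagree with each other, and neither section takes precedence. Two analysts following the plan could analyse different people for the primary endpoint, and the choice could be made after the data are seen. The same population serves the PCS non-inferiority comparison.

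**Working it through.** **1. The two rules side by side**

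| Participant | 9.2 ITT definition | 5.2 app-use rule |
|---|---|---|
| Intervention: installs at baseline visit, uses app | in | in |
| Intervention: installs at baseline visit, never uses it | in | out |
| Intervention: installs only after the visit, uses it | out | in |
| Intervention: never installs | out | out |
| Control | in | not applicable |

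The 5.2 questionnaire rule adds a further conflict. It can remove controls, whereas 9.2 keeps all of them. Its wording can also be read as missing one visit or missing both.

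**2. Does anything else in the plan restore the excluded people?**

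- Per protocol: as worded it has no app criterion, so a non-installer who attends week 16 may be in it. It is still limited to completers, and it is unclear whether 5.2 also applies to it.
- Baseline-adjusted analysis: this changes the model, not the population.
- Multiple imputation: not said to bring excluded people back.
- Missing outcomes: these do not force the exclusion, because ASES and PCS do not depend on the Sidekick app.

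**3. The plan's own figures**

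- Primary: d = 5.5/9.4 = 0.585, two-sided 0.05, 80% power gives 46.83 per arm, 94 in total. 94 × 1.10 = 103.4 (51.7 per arm, stated as 52). 103.4 × 1.15 = 119, stated as 120.
- PCS power with 54 per arm, SD 12.3 and margin 7.7 is 90.2%, as stated.

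The total of 120 is not the problem. The 10% dropout allowance replaces lost numbers but does not remove selection.

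**4. Possible effect on ASES (assumed inputs)**

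Assume no true effect and 60 randomised per arm. A share x = k/60 would not take up the app, and their mean change is d SD worse. The k people are removed from the intervention arm; controls keep the same share. The closed form is shift = x·d / √(1/60 + 1/(60(1−x))), with type I error P(|Z + shift| > 1.96).

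Example, x = 0.10 and d = 1: shift = 0.10/√(1/60 + 1/54) = 0.10/0.1876 = 0.533, giving 8.3%. Simulation (200,000 runs per setting) gives slightly less at this end, because the mixture inflates the control variance:

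| Excluded of 60 | t-test, two-sided (d = 0.5 to 1.0) | Wilcoxon, two-sided | False claim of benefit, t-test (nominal 2.5%) |
|---|---|---|---|
| 1 | 5.0% | 5.0% | 2.7-3.0% |
| 3 | 5.2-5.8% | 5.1-5.6% | 3.4-4.5% |
| 6 | 5.8-7.9% | 5.7-7.6% | 4.5-7.3% |

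If excluded people would instead have done better, the false claim of benefit at 6 of 60 falls to 1.3-0.7%.

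**5. PCS non-inferiority (assumed inputs)**

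SE = 12.3 × √(2/60) = 2.246. Suppose the app worsens PCS by exactly the margin, 7.7, in users and by 0 in non-users. With a share x of non-users kept, P(declare non-inferiority) = Φ(7.7x/2.246 − 1.96): 2.5% at x = 0, 2.9% at 2%, 3.7% at 5%, 5.3% at 10%.

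The last figure is an error rate only for the effect in users. For everyone randomised the true effect is then 7.7 × 0.90 = 6.93, inside the margin. The two sets answer different questions, and for PCS the all-randomised set can be the less conservative one.

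**The case against.** The strongest reply is that the problem may be almost empty in practice. Download is a visit 1 step, a compatible smartphone is an eligibility criterion, and each account carries a study code. Section 6.1 says RAID completion is actively encouraged, so using the app once is a low bar. If a first login counts as use, the two sets may nearly coincide. The remark in section 3 about variable compliance concerns app studies in general, not failure to open an app installed in clinic. With 1 to 3 of 60 excluded, the illustrated inflation is slight. The 7.9% figure needs the whole 10% dropout ceiling to be app non-uptake, plus a full-SD difference; the documents support neither.

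All of that stands as a comment on size, and the figures above should be read that way. It does not remove the defect. The documents do not define use, do not say which rule governs, and label as ITT a set that departs from assigned group in one arm. If few people fail the rules, including them costs almost nothing. It is also fair that redefining ITT is not automatically the cautious choice for PCS, which is why both sets should be shown there.

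**Conclusion.** The concern holds. Section 9.2 contradicts its own ITT principle, 5.2 adds a different rule, and no planned analysis covers everyone randomised. This follows from the text and needs no assumption, and it should be corrected because it concerns the population for the primary endpoint.

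The consequence for the results cannot be sized from the documents. On ASES the bias would favour the app if non-users are less motivated and change less, but that direction is not certain. The illustrations rest on assumed exclusion rates of 1 to 6 in 60 and an assumed 0.5-1.0 SD difference. For PCS the direction is unclear.

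**What to change.** - **9.2:** define ITT as all randomised participants in their assigned group, whether or not the app was installed or used. Keep partly observed participants in it through the planned multiple imputation.
- **5.2:** delete the app-use exclusion. State that the questionnaire exclusion means no data at both visits. That group should be almost empty, since questionnaires are completed at visit 1; report its size.
- **Supplementary analysis:** keep one app-user set, labelled modified ITT, for both ASES and PCS. Choose a single criterion, either installed or used, and say how it is verified (for example, whether a first login counts as use).
- **Per protocol:** state whether it carries any app criterion.
- **Reporting:** give the numbers of non-installers and non-users. Section 13 shows that user-behaviour data are already collected.

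The cost is wording and one supplementary analysis, with no new data collection. The ASES estimate may be slightly less favourable to the app, and some power may be lost. If a share x of the intervention arm gets no effect, the expected difference is 5.5 × (1 − x). At x = 10% that is 4.95, and t-test power with 60 per arm falls from 88.9% to 81.0% (with 54 per arm, from 85.4% to 76.8%), before any non-parametric loss. Here x is again an assumption.

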4.2 Primary endpoints

Difference in mean change of total ASES (Arthritis Self-Efficacy Scale) score from baseline to week 16 ± 2w in the intervention group when compared to the control group. The ASES is a patient-reported questionnaire consisting of 20 items to measure one's arthritis-specific self-efficacy across 2 subscales: self-efficacy for managing pain (PSE, range 5-50), and self-efficacy for controlling other symptoms (OSE, range 6-60). Both scores can be summed to derive a total ASES-score (range 11-110).

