9.1 Sample size

For the primary outcome, we opted for a superiority design aiming to reject the null hypothesis that there would be no difference between the intervention and control groups in the change of the total ASES-score from baseline to week 16. Sample size calculation was based on the previously proposed minimal clinically important difference in the ASES-score, corresponding with a change of 5.5 on either the pain or other symptoms subscale (13,25). Moreover, in a recently published, large prospective study from our research group, including 379 patients with RA, the mean (\pm SD) self-efficacy for pain (PSE) was 31.8 (\pm 8.9) and self-efficacy for other symptoms (OSE) was 42.6 (\pm 9.4) (32). Based on a minimal clinically important difference of 5.5 and population SD of 9.4, an effect size of approximately 0.59 was assumed. Additionally, based on previous research and outpatient clinic attendance experience, we expect dropout rate to be maximally 10% (13,24,33). Following these assumptions and in the setting of a superiority trial, 52 participants are needed in each group to detect a clinically meaningful difference in either PSE or OSE with 80% power and a significance level

of 0.05, while allowing for a 10% dropout rate.

It should be noted that the ASES score was not fully normally distributed in our aforementioned prospective study, implying that non-parametric tests might be needed to analyze the primary outcome. Following a general rule of thumb, sample size was thus increased by 15% to account for the loss of power these non-parametric tests would imply(34). Consequently, a total of 120 participants are needed (60 in each group) for the analysis of the primary outcome, with 80% power and a significance level of 0.05.

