An additional sample size calculation was conducted for the secondary outcome of change in PCS score from baseline in the intervention group compared to the control group. Based on pooled data from the PCS development/validation studies and a French cohort of patients with RA, the population weighted mean (SD) PCS score is estimated at 20.3 (SD 12.3) (27,35,36). Thus, a clinically important difference in the PCS score, previously proposed as greater than 38% change (27,37), would correspond to a change in total PCS score of greater than 7.7/52. Aiming to exclude any (negative) effect of the intervention on change in the PCS score, we chose a non-inferiority design for this outcome. Given that the effect of the intervention on the PCS score is unknown, we chose the aforementioned minimal clinically important difference of 7.7 as the non-inferiority margin. In other words, non-inferiority will be confirmed if the upper bound of the 95% CI for the intervention's effect on PCS remains within a minimal clinically important margin(38). Following these assumptions and allowing for a 10% dropout rate, a total of 82 participants need to be included (41 in both the control and intervention groups) to demonstrate a non-inferior effect of the intervention on the PCS score with 80% power, a minimal clinically important margin and a two-sided significance level of 0.025. When 120 patients are included as per the primary outcome, and assuming a 10% drop-out rate, we should have 90.2% power to demonstrate non-inferiority for this secondary outcome.

Sample size calculations were conducted via R version 4.2.1, using the packages *pwr* and *epiR* (see Appendix B). In summary, a total of 120 patients will need to be included to assess both the primary outcome and the secondary outcome with at least 80% power, including 60 participants in both the control group and in the intervention group.

As described above, the intervention group will then again be randomized in a 1:1-ratio to assess the exploratory outcomes. The trial will thus not be powered for the exploratory analyses.

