- The difference in mean change of total PCS score from baseline to week 16 \pm 2w in the intervention group will be compared to that in the control group, using an unpaired t-test or Wilcoxon rank sum test depending on distribution of the PCS score. As a sensitivity analysis, we will additionally assess the difference between groups in week 16 scores using ANOVA adjusted for the baseline score.

Exploratory endpoints

- The difference in mean change of total ASES score from baseline to week 16 \pm 2w in the intervention arm with weekly RAID questionnaires will be compared to that in the intervention arm with monthly RAID questionnaires, using an unpaired t-test or Wilcoxon rank sum test depending on distribution of the ASES-score. As a sensitivity analysis, we will additionally assess the difference between groups in week 16 scores using ANOVA adjusted for the baseline score.

- The difference in mean change of total PCS score from baseline to week 16 \pm 2w in the intervention arm with weekly RAID questionnaires will be compared to that in the intervention arm with monthly RAID questionnaires, using an unpaired t-test or Wilcoxon rank sum test depending on distribution of

the PCS score. As a sensitivity analysis, we will additionally assess the difference between groups in week 16 scores using ANOVA adjusted for the baseline score.

- The difference in mean change of total IPAQ-S score from baseline to week 16 ± 2w in the intervention group when compared to the control group will be evaluated with an unpaired t-test or Wilcoxon rank sum test depending on distribution of the IPAQ-S score. As a sensitivity analysis, we will additionally assess the difference between groups in week 16 scores using ANOVA adjusted for the baseline score.
- The difference in mean change of total PSQI score from baseline to 16 ± 2w in the intervention group when compared to the control group will be evaluated with an unpaired t-test or Wilcoxon rank sum test depending on distribution of the PSQI score. As a sensitivity analysis, we will additionally assess the difference between groups in week 16 scores using ANOVA adjusted for the baseline score.

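### The unadjusted comparison of change is the main analysis for ASES and PCS; the baseline-adjusted model already planned is more precise than the t-test and gives the mean difference and interval that the rank-sum branch leaves undefined

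*Combined protocol and SAP*

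**What the plan says.** Section 4.2 defines the primary endpoint as "Difference in mean change of total ASES (Arthritis Self-Efficacy Scale) score from baseline to week 16", intervention against control. Section 9.2 states that this difference "will be evaluated with an unpaired t-test or Wilcoxon rank sum test depending on distribution of the ASES-score". For PCS, change is compared "using an unpaired t-test or Wilcoxon rank sum test depending on distribution of the PCS score". Neither sentence adjusts for baseline or centre, although section 4.4 randomizes "using stratified (local) randomization by study center".

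For both outcomes section 9.2 then adds: "As a sensitivity analysis, we will additionally assess the difference between groups in week 16 scores using ANOVA adjusted for the baseline score".

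Section 9.1 treats the rank-based branch as a live possibility for the primary outcome: the "ASES score was not fully normally distributed in our aforementioned prospective study, implying that non-parametric tests might be needed". It raises the sample size by 15% on that account. For PCS, section 9.1 sets the decision rule: "non-inferiority will be confirmed if the upper bound of the 95% CI" stays within the margin, which is 7.7 points. The PCS paragraph of section 9.2 mentions neither an interval nor the margin.

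**The concern.** There are two separate issues.

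The first is precision. Baseline ASES and PCS are collected on everyone and are likely to predict the week-16 score. A change-score t-test uses that information less efficiently than a model with baseline as a covariate. The plan contains such a model but does not rely on it.

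The second is what the rank-sum branch delivers. The Wilcoxon test gives a p-value for a shift between two distributions; it does not estimate a difference in mean change. If that branch is used for ASES, the headline result is not an estimate of the endpoint in section 4.2. If it is used for PCS, section 9.2 does not say which interval is to be set against 7.7. PCS is where the trial looks for harm: section 3 raises the possibility that the app increases catastrophizing, and section 7 gives that as the reason for the non-inferiority setting.

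**Working it through.** **Inputs from the documents** (section 9.1 and Appendix B): PCS SD 12.3, margin 7.7; ASES difference 5.5, SD 9.4; 120 randomized, 10% dropout, so 108 evaluable, 54 per arm. **Assumed, not in the documents:** rho of 0.3, 0.5 and 0.7; equal variances at both visits; the shape of the data in the simulations.

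**The plan's own figures.** ASES: d = 5.5/9.4 = 0.585; two-sided 0.05 and 80% power give 46.83 per group, 94 in total; 94 × 1.10 × 1.15 = 119, against 120 stated. PCS: SE = 12.3 × √(2/54) = 2.367; 7.7/2.367 − 1.96 = 1.293, so power is 90.2%, as stated. This uses one-sided 0.025, which matches a 95% CI. Both calculations put a cross-sectional SD on a change score. Since SD(change) = SD × √(2(1−rho)), that equals assuming rho = 0.5.

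**Change-score t-test against the adjusted model.** Variance of change = 2s²(1−rho). Variance after baseline adjustment = s²(1−rho²). Ratio = (1+rho)/2. CI half-width = t(0.975) × SD × √(2/54). Example at rho 0.3: change SD = 12.3 × √1.4 = 14.55, half-width 5.55; adjusted SD = 12.3 × √0.91 = 11.73, half-width 4.48. Power below is from the noncentral t with no true difference, which is why rho 0.5 gives 89.7% and not the normal-approximation 90.2%.

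| rho | Variance ratio | CI narrower by | PCS half-width, change v adjusted | PCS power, change v adjusted |
|---|---|---|---|---|
| 0.3 | 0.65 | 19% | 5.55 v 4.48 | 77.8% v 92.2% |
| 0.5 | 0.75 | 13% | 4.69 v 4.06 | 89.7% v 96.1% |
| 0.7 | 0.85 | 8% | 3.64 v 3.35 | 98.6% v 99.5% |

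The variance ratio does not depend on scale, so it also applies to total ASES. With the plan's ASES inputs, which are those of a subscale and serve only as illustration, power is 72.1% v 88.5%, 85.4% v 93.6% and 97.3% v 98.8%.

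**Rank-sum test against the adjusted model.** Simulated power at 54 per arm with a shift of 0.585 SD (8,000 to 10,000 trials per setting; skewed data share a gamma component between visits):

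| Shape | rho 0.3 | rho 0.5 | rho 0.7 |
|---|---|---|---|
| Normal | 70% v 88% | 84% v 93% | 97% v 99% |
| Skewness 1.0 | 76% v 88% | 90% v 93% | 99% v 99% |
| Skewness 2.0 | 91% v 88% | 98% v 93% | 100% v 98% |

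**A rank-sum p-value cannot stand in for the PCS interval.** With bounded PCS-like scores (0 to 52, mean 20.3, SD 12.3, rho 0.5, 2,000 trials) and a true worsening of exactly 7.7, the rank-sum test against zero was non-significant in 13% of trials. Comparing an upper bound with 7.7 wrongly declared non-inferiority in 1.8% to 2.5%.

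**Choice of test.** Section 9.2 names the distribution of the score, whereas the change is tested, and gives no check or threshold. Take Shapiro-Wilk at 0.05 as an assumed rule, with skewness 1.0. Checking the baseline score and checking the change then select different tests in 68%, 55% and 30% of trials at the three rho values, but the significance verdict differs in only 4.8%, 2.3% and 0.3%. Type I error when choosing by the score was 0.045 to 0.056, against 0.044 to 0.058 for either test used alone.

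**The case against.** The strongest reply is that the plan is sound and the rest is preference. The t-test on change is unbiased under randomization, estimates the stated endpoint and gives an interval. The adjusted analysis is already promised for both outcomes, so an adjusted mean difference can be reported whichever branch is taken. Section 9.1 commits to a 95% CI for PCS, and the documents report non-normality for ASES only. Every precision gain rests on a rho that the documents do not give.

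Much of this stands. A reader might infer that the rank-sum method cannot yield a bound for PCS. It can: inverting the test gives a Hodges-Lehmann interval. But the plan does not name it, and it concerns a location shift, which equals the difference in mean change only if the two groups' change distributions have the same shape. A reader might also infer that choosing the test from the data inflates type I error; the simulations show no inflation. The missing criterion may be little more than loose wording.

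What does not stand is that adjustment is mere preference. Using a collected baseline value and the randomization stratum is a recognised low-cost improvement, and against the t-test its advantage holds for any rho below 1 under equal variances.

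One caution applies to both analyses. They target the same difference when the groups are comparable at baseline, and sections 5.2 and 9.2 remove some intervention patients after randomization. That is a separate matter, which neither analysis repairs.

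**Conclusion.** The point holds as an avoidable loss of precision and a gap in specification, not as an invalid analysis. Against the t-test, the adjusted model narrows the interval by 19%, 13% or 8% at rho 0.3, 0.5 or 0.7. At rho 0.3 the planned PCS comparison falls to 78% power, below both the 80% target and the stated 90.2%, while the adjusted model keeps 92%. From rho of about 0.7 the gain is small.

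In the rank-sum branch, the headline ASES test does not estimate the endpoint in section 4.2, and section 9.2 leaves the PCS interval unnamed although section 9.1 decides on one. The test-choice criterion is a minor omission.

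A reader might conclude that the adjusted model always has more power. That is not supported: at skewness of about 2.0 the rank-sum test did slightly better, for example 98% v 93% at rho 0.5. The case for the model in that setting is that it estimates the right quantity with an interval. The closed-form results rest on assumed rho and equal variances; the simulated ones also rest on assumed data shapes.

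**What to change.** Before any between-group results are seen, amend section 9.2 as follows.

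- Make the linear model of week-16 score on group, baseline score and centre the single primary analysis for ASES and the analysis for PCS.
- Fix one standard-error method in advance, for example robust standard errors in all cases. Making it conditional on residual skew would bring back a data-dependent choice.
- Report the adjusted mean difference with its 95% CI, pooled where multiple imputation is used, and compare the PCS upper bound with 7.7.
- Keep the t-test and rank-sum test on change as sensitivity analyses.

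If the current tests are kept as the main analysis, the minimum is to state the choice criterion on the change score, fix it before between-group results are seen, and name the interval compared with 7.7 when PCS change is not normal.

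The cost is one protocol amendment. No new data are needed: baseline scores and centre are collected, and the model without centre is already planned. The price is the slight loss of power against the rank-sum test if the scores prove strongly skewed.
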